The project employs a randomized control trial (RCT), in which 360 couples are assigned to the intervention group and 360 couples to a control group between June 1, 2016 and September 30, 2020. Our approach integrates three components (1) a 20-hour evidence-informed couple group program called TOGETHER workshop that integrates relationship education and financial literacy skills, (2) case management (assessment of participant needs, development of Individual and Couple Development Plan, referrals for social and mental health services, and referrals and coordination with job and career enhancement services, linking and coordination of all services as needed), and (3) job and career enhancement services for those who need the services.

The main goals of this project are to promote healthy couple relationships and economic stability and mobility for low-income couples in Northern Virginia, Prince [name], and [name]. The main objectives are: 1) improve personal wellbeing; 2) improve

**couple's relationship skills; 3) improve parenting and co-parenting; 4) improve financial literacy and capability; and 5) improve employability, job placement, and retention skills.**

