**Data collected in paper format wil have been completely entered by the time participants' participation is terminated. Electronic identifiable data will be password protected and kept in VT secure hard drive and it will be deleted two years after funding for this study has been concluded (at present the expectation is to be funded by ACF until 9/30/20. All electronic non-identifiable data will be kept for 15 years for data analysis.**

Intervention and control couples will be paid \$160 for completion of assessments (Pretest: \$40 (\$20/partner), Post-test: \$40 (\$20/partner), Follow-up: \$80 (\$40/partner)). Additionally, intervention couples will be given \$40 gift certificate (\$20/partner) for a local grocery store for attending the Needs Assessment meeting with the case manager. Lastly, after completion of the TOGETHER workshop, intervention couples will receive an incentive, \$30-\$80 in gift cards.

To help remove barriers to participation in the program of intervention couples, childcare support (\$280/couple) are budgeted to recruit and engage participants with children ages below 12 , unless the program is able to provide child care onsite during the workshop. Program staff will provide Childcare Reimbursement forms to participants to be redeemed. At a later date a check will be sent directly to the person(s) providing the childcare while the participants attend program sessions and meetings. The total amount for childcare will not exceed \$280 per couple, and are viewed as a cash equivalent and are therefore taxable. Therefore, In order to obtain childcare reimbursement, participants must complete both the W-9 for tax reporting and the Child Reimbursement forms, and obtain the signature of the childcare provider. They must then submit these completed forms to their case managers. The child care provider must be a licensed child care provider.

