Project: TOGETHER – A Couple's Model to Enhance Relationships and Economic Stability

NCT: 04227405

Initial Plan: 3/29/2018

Revised Plan: 11/18/2021

Data Analysis Plan

As a preliminary analysis, each of the outcome scales was summarized at pre, post, and follow-up assessments, using descriptive statistics (mean, standard deviation, scale reliability) for males and females in the whole sample, the treatment group, and the control group.

The main goal of the present RCT was to examine the effectiveness of the intervention. Intervention couples were expected to report significantly better outcomes than the control group upon completion of the workshop and further improvement or maintenance of such changes at the six-month follow-up. Multilevel models were used to test mean differences across time points within the treatment group and across spouses (a dyadic approach). Data were nested longitudinally within individuals, and then individuals were nested within couples. The non-independence of data longitudinally and within couples is accounted for in the multilevel models (Kenny, Kashy, & Cook, 2006).

All analyses were conducted in R (version 3.4.1; R Core Team, 2018). Between-group differences in change were estimated with a piecewise multilevel growth model using all three-time points. The piecewise growth model was specified where the first piece corresponded to the intervention period (pre-test to post-test) and the second piece corresponded to the post-intervention period (post-test to follow-up). We also tested between-group differences in change from baseline to follow-up (pre-test to follow-up). Because participants did not complete the post-intervention and follow-up surveys at the same time (i.e., participants completed the surveys within specific time windows), time was specified as the number of months between assessments and allowed to vary across participants.

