The multilevel approach utilizes all data from each time point, retaining as much data as possible when attrition occurs. Analyses controlled for demographic variables that have been associated with relationships (for a review, see Karney & Bradbury, 2020) and financial outcomes (Xiao et al., 2015): Race (White = 1 vs. not), marital status (married = 1 vs. not), gender, age, highest level of education, income, length of relationship in years, number of children, and baseline measurement of the outcome variables. We controlled for baseline differences in the outcome measures in the piecewise multilevel growth model by constraining baseline treatment and group to equality (i.e., constrained longitudinal data analysis; Liang & Sieger, 2000). To facilitate the interpretation of results, we computed Cohen's d effect sizes (group mean difference divided by the pooled within-group standard error) and confidence intervals (CI) for all effects. The Benjamini-Hochberg method (1995) was used for adjusting p values for multiple comparisons as recommended by What Works Clearinghouse for controlling the false discovery rate for studies that have multiple outcome variables.

We used multilevel generalized mixed models for attrition analyses where the outcome variable was a binary indicator of missing. Covariates were demographic variables and baseline measures of outcome measures. As in the main analyses, random effects were included to account for the nesting of individuals within couples. Attrition analyses examined if there were significant differences in demographic and outcome variables between all participants that stayed in the study in comparison with those that dropped out. Differential attrition analysis examined if there were significant differences in demographic and outcome variables between the control group's attrition and the intervention group's. Nonetheless, we accounted by any attrition differences by

including demographic variables as covariates and controlling for baseline measures of the outcomes in all of the analyses.

Relatedly, we assessed baseline equivalence across groups for demographics and outcome variables not only in the entire sample (at initial randomization) but also in the analytic sample (retained at follow-up) to evaluate attrition effects. We controlled for baseline differences in demographic and outcome variables in all analyses.

References

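### The SAP defines Cohen's d with a standard error as divisor; it needs a named standard deviation, and the divisor used in the code should be confirmed

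*SAP*

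**What the plan says.** In the Data Analysis Plan the SAP gives the purpose of the effect sizes: "To facilitate the interpretation of results, we computed Cohen's d effect sizes". It defines them as "group mean difference divided by the pooled within-group standard error" and adds "and confidence intervals (CI) for all effects". Neither document defines the effect size anywhere else, and the protocol does not mention effect sizes.

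The preliminary-analysis paragraph of the same plan does name the standard deviation. Each outcome is summarized with "descriptive statistics (mean, standard deviation, scale reliability", at pre-test, post-test and follow-up, for men and women, in the whole sample and in each arm. Nothing links those standard deviations to d.

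The model has three levels: "Data were nested longitudinally within individuals, and then individuals were nested within couples". The SAP names R as the software but gives no package, function or code for d.

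**The concern.** Cohen's d expresses a mean difference in units of the spread between people, which does not depend on how many people were studied. A standard error shrinks as the sample grows, so a difference divided by it grows with the sample. The stated formula therefore does not define the quantity it names.

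Swapping one word would not fully repair it. In a three-level model several standard deviations are available: the raw one at pre-test, the raw one at another assessment, and the model residual. They give d on different scales, and the SAP chooses none of them.

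What is at stake is interpretation. Under literal use, the value and scale of d would depend on the number of respondents. It could not be read on the usual scale or compared with other programs. Under a residual standard deviation, d would look plausible but sit on a different scale from one built on the tabulated standard deviations. The SAP was revised on 11/18/2021 and is written in the past tense, so it stands as the record of what was done.

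**Working it through.** The documents report no d, standard deviation or standard error, so there is no figure to reproduce. The check asks what each reading of the divisor would do to d.

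**Inputs**
- From the protocol's opening section: "360 couples are assigned to the intervention group and 360 couples to a control group". So n = 360 couples, or 2 × 360 = 720 individuals, per arm.
- Assumed, not in the documents: true d = 0.20; 60% retention, giving 0.60 × 360 = 216 couples per arm; partner correlation c = 0.2 to 0.6; pre-post correlation r = 0.5 to 0.7; 50% to 70% of outcome variance carried by random effects.

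**1. Literal standard error, simple two-group comparison (outcome SD = 1)**

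With m independent units per arm, the SE of one mean is 1/√m and the SE of the difference is √(2/m). The printed value is therefore d·√m or d·√(m/2). Partners are correlated, so m lies between n (correlation 1, a couple counts once) and 2n (correlation 0, each partner counts).

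| Divisor | Units | Factor, n = 360 | 0.20 prints as | Factor, n = 216 | 0.20 prints as |
|---|---|---|---|---|---|
| SE of difference | couples | √(n/2) = 13.42 | 2.68 | 10.39 | 2.08 |
| SE of difference | individuals | √n = 18.97 | 3.79 | 14.70 | 2.94 |
| SE of one mean | couples | √n = 18.97 | 3.79 | 14.70 | 2.94 |
| SE of one mean | individuals | √(2n) = 26.83 | 5.37 | 20.78 | 4.16 |

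**2. Literal standard error of the pre-to-post contrast, with baseline means constrained equal**

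For two assessments, SE = √((1 + c)(1 − r²)/n).
- n = 360, c = 0.6, r = 0.5: √(1.6 × 0.75/360) = 0.0577, factor 1/0.0577 = 17.3.
- n = 360, c = 0.2, r = 0.7: √(1.2 × 0.51/360) = 0.0412, factor 24.3.
- n = 216, the same two corners: factors 13.4 and 18.8.

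This is closer to the planned model and falls inside the range in step 1.

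**3. Residual standard deviation**

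If random effects carry a share v of the variance, the residual SD is √(1 − v) and d is multiplied by 1/√(1 − v).
- v = 0.5: factor 1.41, and 0.20 prints as 0.28.
- v = 0.7: factor 1.83, and 0.20 prints as 0.37.

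**4. Slip for standard deviation**

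The factor is 1 if the pooled raw SD was used. The SAP would still have to say at which assessment.

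**The case against.** The strongest reply is that this is a one-word slip. The quantity is called Cohen's d, and pooled within-group is the usual qualifier of a standard deviation. The same part of the SAP has another drafting slip: a method citation is spelled differently in the text and in the reference list. No reported value is shown to be wrong, and values such as 2.7 to 5.4 would be conspicuous to anyone reading the output. Effect sizes are an interpretive aid, and inference does not rest on them. The residual reading is conjecture: it comes from R's habit of labelling a residual SD a residual standard error, not from anything in the SAP.

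Much of this stands. A slip is quite possible, and the large factors belong to one reading only. Any confidence interval depends on sample size, so the abnormality under literal use is in the value and scale of d. The SAP also leaves unclear whether its intervals are for d or for the model effects.

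It does not remove the point. The SAP uses the term standard deviation correctly elsewhere, so a reader cannot take the two terms as interchangeable. A literal error would probably be noticed, but 0.20 printing as 0.28 to 0.37 would not. And even if the word is a slip, the standard deviation is still unnamed.

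**Conclusion.** The concern holds. The definition is wrong as written for every effect size it covers, and the intended divisor is not stated. That much follows from the text alone.

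The numerical effect is conditional on the reading:
- Literal standard error: about 13 to 27 times at the planned size, or 10 to 21 times with the assumed 60% retention.
- Residual standard deviation: about 1.4 to 1.8 times under the assumed variance shares.
- Wording slip: no inflation.

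Only the 360 couples per arm comes from the documents, and it is a planned number before attrition. The review does not show that any computed value is wrong. Model tests, p values and the Benjamini-Hochberg adjustment do not use d. This should be fixed, but it does not threaten the inference.

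**What to change.** First check which divisor the R code used. Then:

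- Replace standard error with standard deviation, and state which one and at which assessment. The pooled within-group SD at pre-test is one acceptable choice; another would serve if it is named.
- Define d as the model-estimated between-group difference in change over a stated interval, divided by that SD. Because time enters the model in months, say how slopes become a difference at post-test and follow-up.
- State that the interval is for d. Dividing the limits of the difference by the same SD gives it; note that this is an approximation, because it treats the SD as known.
- If d is also reported for changes within the treatment group, define it for those separately.
- Recompute only the effect sizes that used a standard error, or an SD other than the one stated.

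The cost is a short change to the SAP and a look at the code. If recalculation is needed, the SDs are already summarized by sex, arm and assessment; a value for both sexes together has to be pooled from these or taken from the raw data. The protocol's data-retention paragraph says: "All electronic non-identifiable data will be kept for 15 years for data analysis". No test or p value changes.
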